7.6.2. Instructions for Reporting Special Situations

7.6.2.1. Instructions for Reporting Pregnancies

The investigator should report pregnancies in female study subjects that are identified after initiation of study medication and throughout the study, to Gilead PVE using the pregnancy report form within 24 hours of becoming aware of the pregnancy.

Refer to the eCRF completion guidelines for full instructions on the mechanism of pregnancy reporting.

The pregnancy itself is not considered an AE nor is an induced elective abortion to terminate a pregnancy without medical reasons.

Any premature termination of pregnancy (eg, a spontaneous abortion, an induced therapeutic abortion due to complications or other medical reasons) must be reported within 24 hours as an SAE. The underlying medical reason for this procedure should be recorded as the AE term.

A spontaneous abortion is always considered to be an SAE and will be reported as such. Furthermore, any SAE occurring as an adverse pregnancy outcome post study must be reported to Gilead PVE.

The subject should receive appropriate monitoring and care until the conclusion of the pregnancy. The outcome should be reported to Gilead PVE using the pregnancy outcome report form. If the end of the pregnancy occurs after the study has been completed, the outcome should be reported directly to Gilead PVE.

Pregnancies of female partners of male study subjects exposed to Gilead or other study drugs must also be reported and relevant information should be submitted to or Gilead PVE using the pregnancy and pregnancy outcome forms within 24 hours. Monitoring of the subject should continue until the conclusion of the pregnancy. If the end of the pregnancy occurs after the study has been completed, the outcome should be reported directly to Gilead PVE.

Gilead PVE:

Fax:

PPD

E-mail:

Refer to [Appendix 4](#) for Pregnancy Precautions, Definition for Female of Childbearing Potential, and Contraceptive Requirements.

7.6.2.2. Reporting Other Special Situations

All other special situation reports must be reported on the special situations report form and forwarded to Gilead PVE within 24 hours of the investigator becoming aware of the situation. These reports must consist of situations that involve study IMP and/or Gilead concomitant medications, but do not apply to non-Gilead concomitant medications.

Special situations involving non-Gilead concomitant medications do not need to be reported on the special situations report form; however, for special situations that result in AEs due to a non-Gilead concomitant medication, the AE should be reported on the AE form.

Any inappropriate use of concomitant medications prohibited by this protocol should not be reported as “misuse,” but may be more appropriately documented as a protocol deviation.

Refer to the eCRF completion guidelines for full instructions on the mechanism of special situations reporting.

All clinical sequelae in relation to these special situation reports will be reported as AEs or SAEs at the same time using the AE eCRF and/or the SAE report form. Details of the symptoms and signs, clinical management, and outcome will be reported, when available.

8. STATISTICAL CONSIDERATIONS

8.1. Analysis Objectives and Endpoints

8.1.1. Analysis Objectives

The primary objective of this study is:

- To determine the preliminary efficacy of the combination of tirabrutinib and idelalisib with obinutuzumab in subjects with relapsed or refractory CLL

The secondary objective of this study is:

- To evaluate the safety and tolerability of the combination of tirabrutinib and idelalisib with and without obinutuzumab

CCI [REDACTED]

[REDACTED]

[REDACTED]

8.1.2. Primary Endpoint

The primary endpoint is the rate of CR per modified IWCLL 2008 criteria {Hallek 2008} at Week 25.

8.1.3. Secondary Endpoints

The secondary endpoints of this study are:

- Rate of CR/BM MRD- at Week 25
- Rate of CR/PB MRD- at Week 25
- ORR at Week 25 including CR, CRi, PR, and PR with lymphocytosis
- Type, frequency, and severity of AEs and SAEs

CCI

[REDACTED]

[REDACTED]

[REDACTED]

[REDACTED]

[REDACTED]

[REDACTED]

[REDACTED]

[REDACTED]

[REDACTED]

[REDACTED]

8.2. Analysis Conventions

8.2.1. Analysis Sets

8.2.1.1. Efficacy

The primary analysis set for efficacy analysis is the Full Analysis Set (FAS), which is defined as all subjects randomized or enrolled to each study arm who received at least 1 dose of any study treatment. Subjects are analyzed according to the study treatment they are assigned to at randomization or enrollment.

The PP analysis set is defined as all randomized or enrolled subjects who received at least 1 dose of any study treatment and had disease assessment at baseline and at least 1 evaluable response assessment post baseline. Study treatment assignment will be designated according to the actual treatment received. This analysis set will be used in the supplementary analysis of response endpoints.

8.2.1.2. Safety

The primary analysis set for safety analyses is the safety analysis set, which is defined as all randomized or enrolled subjects who received at least 1 dose of any study treatment, with study treatment assignment designated according to the actual treatment received.

CCI [REDACTED]

CCI [REDACTED]

8.3. Data Handling Conventions

By-subject listings will be presented for all randomized or enrolled subjects in the FAS and sorted by subject ID number, visit date, and time if applicable. Data collected on log forms, such as AEs, will be presented in chronological order within subject. Summary tables for continuous variables will contain the following statistics: N (number in population), n (number with data), mean, standard deviation, median, minimum, and maximum. Summary tables for categorical variables will include: N, n, and percentage.

The baseline value is generally defined as the last (most recent) pre-treatment value in safety analyses and the last (most recent) pre-randomization value for efficacy analyses. Data from all sites will be pooled for all analyses. If there is a significant degree of non-normality, analyses may be performed on log-transformed data, as appropriate.

In general, missing data will not be imputed. For response endpoints, if a subject is missing baseline or post baseline assessments, the subject will be treated as non-responders. CCI [REDACTED]

[REDACTED] Methods for imputing partially missing dates and laboratory results beyond limit of quantification will be provided in the SAP.

8.4. Demographic Data and Baseline Characteristics

Subject demographic variables (age, sex, race and ethnicity), baseline characteristics (including body weight, height, body mass index, and ECOG Performance Status) as well as baseline disease characteristics (including time since initial diagnosis, disease staging at study entry, cytogenetic risk group, refractory and relapse status) will be summarized descriptively by treatment arms and overall based on the FAS. Medical history and concomitant medication use will be summarized using safety analysis set.

In general, continuous variables will be summarized by sample size, mean, standard deviation, median, quartiles, minimum and maximum and categorical variables will be summarized by counts and percentages.

8.5. Efficacy Analysis

8.5.1. Primary Endpoint

Tumor response will be based on investigator's assessment according to the modified IWCLL 2008 criteria (see [Appendix 6](#)).

Rate of CR will be calculated by treatment arms using the FAS. The 2-sided 90% exact confidence interval (CI) of CR will be estimated using the Clopper-Pearson method.

No inferential test will be performed. The goal of this analysis is to obtain preliminary estimates of the CR rate.

In addition, the analysis of the primary endpoint will be performed using the PP analysis set.

8.5.2. Secondary Endpoints

ORR and rate of CR/MRD- will be estimated for each arm and their associated 90% confidence intervals will be calculated using the exact method.

CCI

CCI

8.6. Safety Analysis

8.6.1. Extent of Exposure

Treatment exposure and compliance will be summarized descriptively by treatment group based on safety analysis set. Summaries will include treatment duration, number of doses, average dose, dose modifications, and treatment adherence rate.

8.6.2. Adverse Events

Clinical and laboratory adverse events (AEs) will be coded using the current version of Medical Dictionary for Regulatory Activities (MedDRA). The severity of AEs will be graded according to the NCI-CTCAE, Version 4.03. The relationship of the AE to the study treatment will be assessed by the investigator as related or unrelated.

All AEs will be listed. The focus of AE summarization will be on treatment-emergent AEs (TEAEs). A TEAE is defined as an AE that occurs or worsens in severity on or after the date of the first dose of study treatment but no later than 30 days after the last dose of study treatment.

Summaries (number and percentage of subjects) of treatment-emergent adverse events (by SOC and PT) will be provided by treatment group:

- All TEAEs
- TEAEs of Grade 3 or above
- All treatment-related AEs
- Treatment-related AEs of Grade 3 or above
- All treatment-emergent SAEs
- All treatment-related SAEs
- All AEs leading to premature discontinuation of study drug
- All AEs leading to dose modification or temporary interruption of study drug
- All SAEs leading to death (ie, outcome of death)

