1.1. Study Objectives

The primary objective of this study is:

- To determine the preliminary efficacy of the combination of tirabrutinib and idelalisib with obinutuzumab in subjects with relapsed or refractory chronic lymphocytic leukemia (CLL)

The secondary objective of this study is:

- To evaluate the safety and tolerability of the combination of tirabrutinib and idelalisib with and without obinutuzumab

CCI

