7.1.6.1. Summaries of AE Incidence by Severity

The number and percentage of subjects who experienced at least 1 TEAE will be provided and summarized by SOC, HLT, PT, and treatment group. For the AE categories described below, summaries will be provided by SOC, PT, maximum severity, and treatment group:

- TEAEs
- TEAEs with Grade 3 or higher
- TEAEs related to tirabrutinib
- TEAEs related to idelalisib
- TEAEs related to obinutuzumab

- TEAEs related to tirabrutinib with Grade 3 or higher
- TEAEs related to idelalisib with Grade 3 or higher
- TEAEs related to obinutuzumab with Grade 3 or higher
- TE SAEs
- TE SAEs related to tirabrutinib
- TE SAEs related to idelalisib
- TE SAEs related to obinutuzumab
- TEAEs leading to discontinuation of tirabrutinib
- TEAEs leading to discontinuation of idelalisib
- TEAEs leading to discontinuation of obinutuzumab
- TEAEs leading to dose modification of tirabrutinib
- TEAEs leading to dose modification of idelalisib
- TEAEs leading to dose modification of obinutuzumab
- TEAEs leading to temporary interruption of tirabrutinib
- TEAEs leading to temporary interruption of idelalisib
- TEAEs leading to temporary interruption of obinutuzumab
- TEAEs leading to discontinuation of study
- TEAEs leading to death (note that the severity will not be shown as all the TEAEs are Grade 5)

A brief, high-level summary of AEs described above will be provided by treatment group and by the number and percentage of subjects who experienced the above AEs. This summary table will also include TEAEs with Grade 3 or 4 and all deaths.

Multiple events will be counted only once per subject in each summary. Adverse events will be summarized and listed first in alphabetic order of SOC and then by PT in descending order of total frequency within each SOC. For summaries by severity, the most severe severity will be used for those AEs that occurred more than once in a given subject during the study.

In addition to the above summary tables, TEAEs, TEAEs of Grade 3 or higher, TE treatment-related AEs, and TE SAEs will be summarized by PT only in descending order of total frequency.

In addition, data listings will be provided for the following:

- All AEs, indicating whether the event is treatment emergent
- All AEs with Grade 3 or higher
- All SAEs
- All Deaths
- AEs leading to death
- AEs leading to discontinuation of study drug
- AEs leading to discontinuation of study

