7.7. Changes From Protocol-Specified Safety Analyses

There are no deviations from the protocol-specified safety analyses.

CC [REDACTED]

[REDACTED]

[REDACTED]

[REDACTED]

[REDACTED]

[REDACTED]

[REDACTED]

[REDACTED]

[REDACTED]

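### The SAP gives four protocol-specified adverse-event summaries only drug by drug, so no planned AE summary table reports the combination's rate, and SAP 7.7 does not declare the change

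*Protocol*

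**What the plan says.** Protocol 8.6.2 lists AE summaries as number and percentage of subjects, by SOC and PT and by treatment group. Four entries matter here: "Treatment-related AEs of Grade 3 or above", "All treatment-related SAEs", "All AEs leading to premature discontinuation of study drug" and "All AEs leading to dose modification or temporary interruption of study drug". The same section has the investigator judge each AE as related or unrelated to the study treatment, with no split by drug.

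SAP 7.1.6.1 replaces each entry with single-drug rows. An example is "TEAEs leading to discontinuation of tirabrutinib", followed by the same row for idelalisib and for obinutuzumab. The high-level summary covers the categories listed above it and adds only Grade 3 or 4 TEAEs and all deaths.

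Two kinds of output stay at the level of the whole regimen. First, SAP 7.1.6.1 says that "TE treatment-related AEs, and TE SAEs will be summarized by PT only in descending order of total frequency". Second, SAP 7.1.7 plans discontinuation and dose-change summaries across drugs, but only for the seven AEs of interest.

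SAP 7.7 then states: "There are no deviations from the protocol-specified safety analyses".

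**The concern.** The study has one secondary objective: "To evaluate the safety and tolerability of the combination of tirabrutinib and idelalisib with and without obinutuzumab". For a three-drug regimen in about 30 subjects, a reader will ask how many had a severe related AE, a related SAE, or an AE that stopped or changed any part of the treatment. The protocol planned one table for each of these questions. The SAP answers each question separately per drug, and the separate answers do not combine into the planned one.

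The change is also undeclared. SAP 6.4 records departures from the protocol's efficacy analyses, while SAP 7.7 says that there are none for safety. Someone who checks the report against the protocol would find planned tables absent without explanation.

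**Working it through.** No sample-size or error-rate figure is at issue, so there is no stated number to reproduce. The check is a line-by-line comparison of the two table lists, followed by a bound.

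**Step 1: the two lists.**

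| Category | Protocol 8.6.2 | SAP 7.1.6.1 | Kept across drugs in the SAP |
|---|---|---|---|
| Related, Grade 3 or above | 1 | 3 (one per drug) | none |
| Related SAEs | 1 | 3 | none |
| Leading to discontinuation | 1 | 3 | AEs of interest only (7.1.7) |
| Leading to dose change | 1 (modification and interruption combined) | 6 (3 modification, 3 interruption) | AEs of interest only (7.1.7) |
| Related, any grade | 1 (SOC and PT) | 3 | 1, by PT only |

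The first four protocol tables become 3 + 3 + 3 + 6 = 15 single-drug tables. With the fifth row, five become 15 + 3 = 18.

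**Step 2: do the counts overlap?** Protocol 6.5 lets one oral agent be stopped while the other continues, and lets obinutuzumab stop while the oral agents continue. Tables 6-2 and 6-3 also contain events for which all study medication is withheld or stopped. Under SAP 7.1.3 the case report form asks about relationship separately for each drug, so one event can be related to several. Overlap can therefore range from none to complete.

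**Step 3: what three counts can tell.** If a, b and c subjects have the event for each drug, the number with it for at least one drug lies between max(a, b, c) and min(n, a + b + c). The counts below are assumed for illustration, with n = 30, the planned size of Arm B.

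| Per-drug counts | Lower bound | Upper bound | Range |
|---|---|---|---|
| 3, 3, 3 | 3 | 9 | 10% to 30% |
| 6, 6, 6 | 6 | 18 | 20% to 60% |
| 6, 9, 3 | 9 | 18 | 30% to 60% |
| 9, 9, 9 | 9 | 27 | 30% to 90% |

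Direct enumeration for 6, 6, 6 confirms the ends: three identical sets give 6 subjects, three disjoint sets give 18. Dose changes need six counts to be combined. If all six are 3, the range is 3 to 6 × 3 = 18 subjects, or 10% to 60%.

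**Step 4: an example from the protocol itself.** Protocol 1.4 reports a terminated Phase 3 study of idelalisib with obinutuzumab, in which 32 subjects received the combination. Three stopped idelalisib for an AE, one of them for Grade 3 sepsis, and one stopped obinutuzumab for Grade 3 sepsis. That text does not settle whether 3/32 (9.4%) or 4/32 (12.5%) stopped at least one drug.

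**The case against.** The strongest reply is that little is lost. SAP 7.1.6.1 plans listings of all AEs, Grade 3 or higher AEs, SAEs, and AEs that led to stopping study drug; the last runs across drugs. SAP 7.1.3 implies that by-subject listings show relationship. With about 36 subjects, a hand count is feasible for discontinuations, and probably for related Grade 3 or higher AEs and related SAEs. This stands. A reader might infer from the missing tables that the combination's rates cannot be obtained at all; the documents do not support that. Dose changes are the least certain, since the SAP does not say that the AE listing shows the action taken. SAP 4.2.1 plans a count of subjects with reductions or interruptions and the reasons, but it is not an AE table by SOC and PT, and it does not say whether it runs across drugs.

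A second reply is that the protocol's term for study drug could already mean drug by drug, which would suit a design in which agents stop separately. This does not stand. The SAP uses the generic term in 7.1.7 and in its discontinuation listing, beside rows that name a drug, so it treats the two levels as different.

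A third reply is that the protocol's safety endpoint is the type, frequency and severity of AEs and SAEs (Protocol 8.1.3), and that the SAP serves it across the regimen with tables of TEAEs, Grade 3 or higher TEAEs, serious TEAEs and deaths. This stands. A reader might infer that the SAP fails to deliver the tolerability result; no document defines tolerability by the four missing rates alone.

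**Conclusion.** The concern holds for planned summary tables. For related Grade 3 or higher AEs, related SAEs, AE discontinuations and AE dose changes, the protocol plans a table for the treatment as a whole, and the SAP plans only single-drug ones outside the AEs of interest. Related AEs of any grade lose their breakdown by SOC across drugs and keep one by PT. The single-drug counts cannot be added.

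The size depends on the overlap, which is unknown. The ranges in the working rest on assumed counts and describe a reader who has only the summary tables; for discontinuations the planned listing would give the exact number. This is an omission of protocol-specified output in a descriptive study, with no effect on the primary endpoint. The statement in SAP 7.7 is inaccurate and needs correcting in any case.

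**What to change.** In SAP 7.1.6.1, add tables by SOC and PT, and matching rows in the high-level summary, for:

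- TEAEs related to any study drug
- TEAEs of Grade 3 or higher related to any study drug
- serious TEAEs related to any study drug
- TEAEs leading to discontinuation of any study drug
- TEAEs leading to dose modification or interruption of any study drug

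Use the definition of related in SAP 7.1.3, which already spans the three drugs, and count each subject once. Keep the single-drug tables and describe them as additional to the protocol. Reword SAP 7.7 to say so. If the SAP is not reopened, SAP 1 already provides for documenting later changes in the study report, and the added tables can be recorded there.

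The cost is five tables and a few summary rows, programmed from data already collected.

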8.6.3. Laboratory Evaluations

Safety laboratory results will be graded according to NCI-CTCAE Version 4.03. Summaries of laboratory data will be provided for the safety analysis set and will include data collected up to the last dose of study drug plus 30 days. The analysis will be based on values reported in conventional units.

Descriptive statistics will be provided by treatment groups for each safety laboratory test as follows:

- Baseline values (defined as the last measurement obtained on or prior to the date/time of first dose of study drug)
- Post baseline maximum value
- Change from baseline to post baseline maximum value
- Post baseline minimum value
- Change from baseline to post baseline minimum value

In addition, treatment-emergent laboratory abnormalities will be summarized descriptively using number and percentages of subjects by treatment group for the following:

- Grade 3 or 4 laboratory abnormalities
- Shift from baseline in laboratory toxicity grade

Subjects will be categorized according to the most severe post baseline abnormality grade for a given lab test.

CCI

CCI

8.9. Sample Size

The primary goal of the study is to evaluate the efficacy of the combination treatment described above. The evaluation will be based on the estimation of the CR rate and its corresponding exact confidence interval for each arm. Approximately 30 subjects will be enrolled into Arm B, which will result in the 90% confidence interval of the observed CR rate to be within $\pm 17.0\%$. The 90% confidence interval for a given observed CR rate is shown in the table below.

Table 8-1. 90% Confidence Intervals at Different CR Rates

Sample Size	CR Rate	95% Confidence Interval using Clopper-Pearson Method
30	20%	(9.1%, 35.7%)
30	30%	(16.6%, 46.5%)
30	40%	(25.0%, 56.6%)
30	50%	(33.9%, 66.1%)
30	60%	(43.4%, 75.1%)

With Amendment 3, randomization was discontinued. All subsequently enrolled subjects will enter Arm B. A total of approximately 6 subjects in Arm A and 30 subjects in Arm B will be enrolled, thus the total sample size for the study will be approximately 36 subjects.

8.10. External Data Monitoring Committee

No external independent Data Monitoring Committee is used in this study.

8.11. Endpoint Adjudication Committee

No independent endpoint adjudication committee is used in this study.

9. RESPONSIBILITIES

9.1. Investigator Responsibilities

9.1.1. Good Clinical Practice

The investigator will ensure that this study is conducted in accordance with the principles of the Declaration of Helsinki (as amended in Edinburgh, Tokyo, Venice, Hong Kong, and South Africa), International Conference on Harmonisation (ICH) guidelines, or with the laws and regulations of the country in which the research is conducted, whichever affords the greater protection to the study subject. These standards are consistent with the EU Clinical Trials Directive 2001/20/EC and Good Clinical Practice Directive 2005/28/EC.

The investigator will ensure adherence to the basic principles of Good Clinical Practice, as outlined in 21 CFR 312, subpart D, “Responsibilities of Sponsors and Investigators” 21 CFR, part 50, 1998, and 21 CFR, part 56, 1998.

The investigator and all applicable sub-investigators will comply with 21 CFR, Part 54, 1998, providing documentation of their financial interest or arrangements with Gilead, or proprietary interests in the investigational drug under study. This documentation must be provided prior to the investigator’s (and any sub-investigator’s) participation in the study. The investigator and sub-investigator agree to notify Gilead of any change in reportable interests during the study and for 1 year following completion of the study. Study completion is defined as the date when the last subject completes the protocol-defined activities.

